#### **5.4** Assessment Windows

### **5.4.1 Study Day**

When study day is used for display or in comparisons the following algorithm will be used:

- study day = date of assessment date of first dose +1, if date of assessment ≥ first dose date
- study day = date of assessment date of first dose, if date of assessment < first dose date.

Note that the date of first dose is Day 1 and the day before the date of first dose is Day -1 (there is no Day 0).

### 5.4.2 Visit Slotting Algorithm

For all safety and efficacy parameters to be summarized or analyzed by visit, data records will be slotted to one of the protocol specified visits using the following algorithm:

- a) Determine the study day for all records using the algorithms from Section 5.4.1
- b) For all records (including unscheduled visit records, early withdrawal records and repeat visit records), use the study day determined above with the slotting intervals in the analysis visit window table below to slot the record to the appropriate analysis visit.

Final – 22November2011 CONFIDENTIAL Page 17 of 30

**Table 2: Analysis Visit Windows** 

Scheduled Visit	Target Study Day of Visit	Slotting Intervals
Week -5 (Screening)	-35	<=-25
Week -2	-14	-24 to -4 days
Baseline (Week 0)	1	-3 to 1 days
Week 2	15	2 to 29 days
Week 6	43	30 to 64 days
Week 12	85	65 to 106 days
Week 18	127	107 to 148 days
Week 24	169	149 to 211 days
Week 36	253	212 to 295 days
Week 48	337	296 to 379 days
Week 60	421	380 to 463 days
Week 72	505	464 to 547 days
Week 84	589	548 to 631 days
Week 96 (End of Treatment	673	632 to (last dose date)
Visit)*		
Week 97**	680	>Last dose date + 7 days
1 Week Follow-up Visit**	Last dose date + 7 days	>Last dose date + 7 days

\* Week 96 is the end of treatment visit for those subjects completing the study per protocol. For subjects who withdraw early from active treatment, the end of treatment visit will be assigned to an analysis visit based on the visit slotting algorithm using study day.

For parameters which were not scheduled to be collected at all visits, still use the all-inclusive visit intervals defined for all visits (that is, the visit window table above) to slot records. However, if a value is slotted to a visit unscheduled for a parameter, it will not be summarized except for summaries focusing on extreme values such as laboratory shift tables. These records will also be included in data listings.

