7.3.7 Visit 15 – Exit Visit (week 97)

Follow-up is planned at approximately one week after the last dose is administered. If subjects have an ongoing adverse event, the subject will be followed until the adverse event is resolved or returns to baseline. All possible attempts will be made to document resolution of acute and chronic toxicities. Diary and SMBG review

- Physical examination
- Vital Signs: blood pressure, pulse, temperature, respiratory rate taken in the sitting position after at least 5 minutes of rest. Blood pressure must be measured twice with at least 3 min apart
- 12 lead ECG taken in the supine position after at least 5 minutes of rest
- Blood draw for hematology (CBC with platelets, WBC with differential), serum chemistry including FPG, and coagulation as detailed in section 6.7.1
- Urinalysis
- Assess adverse events and record concomitant medications

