  - V8-V15 and ET: CBC, electrolytes, BUN, creatinine, Lipids (TG, TC, HDL-c), ALT, AST, bilirubin (total and direct), HbA1c, FPG. PT only at V8, and V15 or ET.
-  Clean catch sample to be collected at each visit and sent to the central lab. Urine drug screen on screening (visit 1). On-site urine dipstick to be performed at all visits except V2.
- NMP22 testing will be performed at screening (V1), randomization (V3), and at weeks 24 (V8), 48 (V10), 72 (V12), and 96 (V14) or when clinically indicated. For subjects who do not have baseline NMP22 testing following Protocol Amendment 1 (11 April, 2011), NMP22 testing will be performed in the next visit or within 4 weeks after Amendment is approved, whichever comes first.
- Adverse events of special interest are specified to be:
  - Cardio- and cerebro- vascular events,
  - Genitourinary infections
  - Increase in creatinine from baseline by 0.5 mg/dL or more
  - Increase in ALT, AST or bilirubin to >3x ULN
- Visit to be conducted one week after last dose of study drug whether subject early terminates from study or completes V14.

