#### **5.4.3** Multiple Evaluations

After all the records have been slotted based on study day, if there are multiple valid records for an assessment within an assigned analysis visit, only one of these records will be used for summary statistics and analyses. The record to be used is determined using the following hierarchy (in decreasing order):

- the record closest to the target visit day
- the record with an original nominal visit that matches the analysis visit

\*\* Week 97 is the 1 week post-treatment follow-up visit for those subjects completing the study per protocol. The 1 Week Follow-up Visit is the 1 week post-treatment follow-up visit for those subjects who withdraw early from active treatment.

• the record earliest in time

For missing values prior to Week 24 where the LOCF algorithm is applied, it is always the last valid assessment on treatment carried forward even though this might not be the assessment obtained by the above hierarchy and used in the summaries by visit.

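### SAP Table 2 opens both follow-up slots only after last dose + 7 days, so the scheduled follow-up day never enters one, and no last-dose day admits both the Week 96 and Week 97 targets

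*SAP*

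**What the plan says.** SAP 5.4.1 sets the first dose as Day 1. Step (b) of 5.4.2 then places records by study day alone: "For all records (including unscheduled visit records, early withdrawal records and repeat visit records), use the study day determined above", matched against the intervals in Table 2. It states no exception for follow-up visits.

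The last three rows of Table 2 matter here:

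- Week 96: target Day 673, interval "632 to (last dose date" (the bracket closes after the last word).
- Week 97: target Day 680, interval ">Last dose date + 7 days".
- 1 Week Follow-up: target last dose + 7 days, with the same interval as Week 97.

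The single-asterisk footnote covers early withdrawals: "the end of treatment visit will be assigned to an analysis visit based on the visit slotting algorithm using study day". The double-asterisk footnote divides the follow-up rows: "Week 97 is the 1 week post-treatment follow-up visit for those subjects completing the study per protocol", and the other row serves early withdrawals.

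On timing, footnote 8 of SAP Table 1 has "Visit to be conducted one week after last dose of study drug whether subject early terminates from study or completes V14". Protocol 7.3.7 is slightly looser: "Follow-up is planned at approximately one week after the last dose is administered". Footnote 4 of SAP Table 1 shows what is drawn: "V8-V15 and ET: CBC, electrolytes, BUN, creatinine, Lipids (TG, TC, HDL-c), ALT, AST, bilirubin (total and direct), HbA1c, FPG".

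SAP 5.4.3 uses the nominal visit only to choose among records already in the same slot, and only after closeness to the target day.

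**The concern.** The 1 Week Follow-up row excludes its own target, which is the day on which the schedule asks for the visit. Section 5.4.2 is meant to send each record to one protocol visit. As printed, some records get no slot and others get two, with no precedence rule. The tie-breakers in 5.4.3 work only inside a slot, so they can neither recover an unplaced record nor choose between slots.

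Two things are at stake. First, the table shells in Appendix 1 ask for Week 97 and 1 Week Follow-up results for HbA1c, FPG and safety laboratory tests. Under the printed rule those columns hold only visits later than L+7. Second, the Week 2 to Week 84 intervals are not cut off at the last dose. An early withdrawal's follow-up value can therefore sit in an on-treatment week. The observed-case analyses (7.2) and the repeated-measures model (7.3.1) exclude only post-rescue values, so nothing there removes it.

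**Working it through.** **Inputs.** All come from SAP 5.4.1 and Table 2. L is the study day of the last dose. On-treatment intervals run without gaps from Day 2 to Day 631 (Week 2 to Week 84). Week 96 is Day 632 to L. Both follow-up slots require day > L+7.

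**Reproducing the printed targets.** With first dose on Day 1, target = 7 × week + 1. Week 96: 7 × 96 + 1 = 673. Week 97: 7 × 97 + 1 = 680. The formula gives all 12 numeric post-baseline targets in Table 2.

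**Step 1: a visit on L+7.** The follow-up slot needs L+7 > L+7, which is false for every L.

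- It falls in Weeks 2 to 84 if L+7 ≤ 631, so L ≤ 624.
- Otherwise L+7 ≥ 632, but it is later than L, so Week 96 does not take it. For L ≥ 625 it has no slot.

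**Step 2: a visit on L+8.** It always satisfies the follow-up condition. It also lies in Weeks 2 to 84 if L+8 ≤ 631, so L ≤ 623. Those records match two slots.

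**Step 3: both printed targets.** Day 673 enters Week 96 only if L ≥ 673. Day 680 enters Week 97 only if 680 > L+7, so L ≤ 672. The conditions exclude each other.

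| L | Day 673 | Day 680 |
|---|---|---|
| 672 | no slot | Week 97 |
| 673 | Week 96 | no slot |

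**Step 4: reach into Week 24.** The Week 24 slot is Days 149 to 211. An L+7 record enters it for L = 149 − 7 = 142 to 211 − 7 = 204, which is 63 values. Slot entry is not selection, because 5.4.3 takes the record closest to Day 169. Assume there is also an on-drug record on day L.

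- L = 142 to 148: the day-L record belongs to Week 18 (Days 107 to 148), so L+7 does not compete with it.
- L = 149 or later: L+7 wins only if |L + 7 − 169| < |L − 169|, so L < 165.5. At L = 165 the distances are 3 and 4; at L = 166 they are 4 and 3.

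Under that assumption L+7 is selected only for L = 142 to 165, which is 24 values.

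**Step 5: would a smaller edit do?** Changing > to ≥ puts L+7 in follow-up for every L, but admits both targets only at L = 673. It still leaves Day 673 unslotted at L = 672. Opening follow-up at > L admits both for L = 673 to 679, but at L = 672 sends Day 673 to follow-up. Neither edit removes the double match for early withdrawals.

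**The case against.** The best case against the point is that this is a drafting slip with little reach. The intent is readable from the double-asterisk footnote. The affected by-visit results are secondary or descriptive, their p-values are nominal under 5.2, and all data stay in the listings. Targets are not entry criteria, since 5.4.3 uses them only to rank records already slotted. The Week 96/97 conflict also depends on where L falls for a completer. L = 672 follows from 96 × 7 daily doses starting on Day 1, but SAP 8.2 has dosing run through Week 96 and does not say whether a dose is taken on the visit day.

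Much of this stands. It limits the size of the point and shows that the Week 96/97 part is not urgent. It does not repair the rule. The footnote says which subjects own which visit, without giving an interval or an exception to study-day slotting, and two programmers could resolve it differently. Whether L is 672 or 673, one printed target still misses its slot.

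A reader might infer that off-drug HbA1c values enter the primary analysis at Week 24. The documents do not support that as a general conclusion. SAP 5.3.1 carries forward observations recorded on treatment, and 5.4.3 repeats that limit even where the by-visit hierarchy would pick another record. What remains is loose wording: 7.1 refers to the last post-baseline value without the on-treatment limit, and 5.4.3 speaks of missing values, which a slotted off-drug value is not. Nor should one infer that all follow-up data are lost, because visits after L+7 do enter the slot.

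**Conclusion.** The rule is wrong as written and should be corrected. Its boundaries are exact on the printed text: L+7 never enters a follow-up slot; it is unslotted for L ≥ 625 and only in an on-treatment week for L ≤ 624; L+8 matches two slots for L ≤ 623; and no L admits both Day 673 and Day 680 to their own slots.

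The consequence falls on the by-visit Week 96, Week 97 and 1 Week Follow-up outputs, and on the observed-case and repeated-measures analyses where an early withdrawal's off-drug value may be treated as on-drug. Primary-analysis exposure is limited to the wording gap. Slot entry is possible for L = 142 to 204, and selection narrows to L = 142 to 165 if an on-drug record exists on day L, which is an assumption. The documents do not give the number of subjects affected, and no effect on a treatment estimate is claimed.

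**What to change.** Slot by study day relative to L:

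1. End every on-treatment interval, including Week 96, at L+1. This allows an end-of-treatment visit on the day after the last dose.
2. Start the follow-up slot at L+2: Week 97 for completers, 1 Week Follow-up for early withdrawals.
3. Keep the on-treatment limits in 5.3.1 and 5.4.3, add the same limit to the carry-forward sentence in 7.1, and define on-treatment as drawn on or before L+1, never by slot.

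Check: any post-baseline day is either ≤ L+1 or ≥ L+2, so each record has exactly one slot. L+7 is always in follow-up. Day 673 needs 673 ≤ L+1 (L ≥ 672) and Day 680 needs 680 ≥ L+2 (L ≤ 678), so both enter their own slots for L = 672 to 678.

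Slotting by visit label would be less safe. SAP Table 1 uses V15 for completers and early terminators and also names ET, while Protocol Appendix 1 has an ET column and no V15. A label rule with no limit relative to L could also place an end-of-treatment record from Day 160 in Week 24 for a subject with L = 100, 60 days off drug.

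The cost is a few SAP lines and one derivation change. First and last dose dates and completion status are already in Listing 16.2-1.1. The downside is that an end-of-treatment visit after L+1 moves to follow-up, so the single-asterisk footnote must be reworded to match. Adopt the early-withdrawal rule before the Week 24 unblinding, and the Week 96/97 bounds no later than final database lock.

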7 STUDY ACTIVITIES

The study activities in each clinic visit are listed below and are presented in Appendix A. Screening period may last up to 21 days (Visit 1 to Visit 2), Run-in period is to be 14 ± 3 days (Visit 2 to Visit 3), Visit 3 to Visit 4 window is 14 ± 3 days. All other visit windows are the nominal duration from randomization ± 7 days.

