7.1.1 Visit 1 - Screening (weeks –5 to -2)

The screening can be performed up to 3 weeks from the start of study activities. During the screening period, the following information will be gathered or the indicated procedure will be performed:

- Informed Consent and medical history obtained, and Inclusion/Exclusion criteria evaluated
- Complete physical examination including height and weight
- Vital Signs: blood pressure, pulse, temperature, respiratory rate taken in the sitting position after at least 5 minutes of rest. Blood pressure must be measured twice with at least 3 min apart
- 12 lead ECG taken in the supine position after at least 5 minutes of rest
- Blood draw for hematology (CBC with platelets, WBC with differential), serum chemistry including FPG, and coagulation as detailed in section 6.7.1
- Urinalysis
- Urine screen for drugs of abuse. Drug screening includes amphetamines, barbiturates, cocaine metabolites, opiates, benzodiazepines, and cannabinoids.
- Urine pregnancy test (only for females who are not postmenopausal)
- The subject must be queried to assess compliance with a minimum of a 10 h fast prior to blood draw to ensure the FPG values can be accurately determined. If a subject has not fasted for 10 h, the subject should return within a week after proper fasting.

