**Table 1: Schedule of Events** 

		ening un-in		Treati	nent w	eeks 1	to 24			Treati	nent w	eeks 25	to 96		Follow Up 
Visit Number	1	2	3	4	5	6	7	8	9	10	11	12	13	14	15
Time to Randomization Visit (weeks) 	-5	-2	0	2	6	12	18	24	36	48	60	72	84	96	1 wk f/u
Informed Consent	X														
Screening for I/E criteria	X	X	X												
Medical History	X														
Diet & exercise counseling 		X				X		X		X		X			
Diary & glucometer record review			X	X	X	X	X	X	X	X	X	X	X	X	X
Discontinue anti-diabetic medication		X													
Randomization			X												
Physical exam 	X					X		X		X		X		X	X
Vital signs	X	X	X	X	X	X	X	X	X	X	X	X	X	X	X
ECG	X		X					X			X			X	X
Dispense study medication		X	X		X	X	X	X	X	X	X	X	X		
Blood draw for clinical lab test 	X		X	X	X	X	X	X	X	X	X	X	X	X	X
Urinalysis 	X		X	X	X	X	X	X	X	X	X	X	X	X	X
NMP22 testing 	X		X					X		X		X		X	
$AE^7$			X	X	X	X	X	X	X	X	X	X	X	X	X
Con Med		_	X	X	X	X	X	X	X	X	X	X	X	X	X

Screening period may last up to 21 days (V1 to V2), Run-in period is to be 14±3 days (V2 to V3), V3 to V8 window is ±3 days, all other visit windows are the nominal duration from randomization ± 6 days.

Glucose meter will be dispensed at visit 2. Training on using glucometer and recording hyper- or hypoglycemia will be conducted on visit 2.

- A complete physical examination will be performed by the investigator at screening and at the termination visit. An abbreviated physical examination will include body weight and general assessment of the skin, heart, lungs and abdomen. Abbreviated physical examinations will be performed by the investigator at all other time points, unless clinically indicated.
-  Blood sample for these lab tests at the designated visit are listed as following. Fasting state must be confirmed.
  - V1: CBC, electrolytes, BUN, creatinine, Lipids (TG, TC, HDL-C), ALT, AST, bilirubin (total and direct), PT, HbA1c, FPG, TSH, Hepatitis Screen (HBsAg, HBcAb, HCV), serum pregnancy for women of childbearing potential
  - V3: CBC, electrolytes, BUN, creatinine, Lipids (TG, TC, HDL-c), ALT, AST, bilirubin (total and direct), HbA1c, FPG
  - V4: CBC, electrolytes, BUN, creatinine, HbA1c, FPG
  - V5: CBC, electrolytes, BUN, creatinine, HbA1c, FPG
  - V6: CBC, electrolytes, BUN, creatinine, Lipids (TG, TC, HDL-c), ALT, AST, bilirubin (total and direct), HbA1c, FPG
  - V7: CBC, electrolytes, BUN, creatinine, HbA1c, FPG

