## Table 14.2-1.5 Summary Statistics for HbA1c (%) (Full Analysis Set - OC)

Screening

	EGT0001442 (N=xxx)	Placebo (N=xxx)
Number of Subjects [1]	xxx	xxx
Screening Mean (SD)	xx.xx (xx.xxx)	xx.xx (xx.xxx)
Median	XX.XX	XX.XX
Min, Max	xx.x, xx.x	xx.x, xx.x

Note: This summary uses all observed values; no missing data imputation is performed. Baseline is defined as the last available assessment on or prior to the first dose of study drug.

[1] For Screening and Week 0 the number of subjects with a value at the specified visit is displayed. For all post-baseline visits, the number of subjects with a value at baseline and at the specified visit is displayed. Source Data: Listing 16.2-7.1

Programming Note: Use page 1 shell for Screening and Week 0, use pages 2 shell for the remaining post-baseline visits (Weeks 2, 6, 12, 18, 24, 36, 48, 60, 72, 84, 96, 97 and 1 week follow-up).

Protocol: THR-1442-C-418 Page x of y

Table 14.2-1.5

Summary Statistics for HbA1c (%)

(Full Analysis Set - OC)

Week 2

	EGT0001442 (N=xxx)	Placebo (N=xxx)
Number of Subjects [1]	xxx	xxx
Baseline		
Mean (SD)	xx.xx (xx.xxx)	xx.xx (xx.xxx)
Median	xx.xx	xx.xx
Min, Max	xx.x, xx.x	xx.x, xx.x
Week 2		
Mean (SD)	xx.xx (xx.xxx)	xx.xx (xx.xxx)
Median	xx.xx	xx.xx
Min, Max	xx.x, xx.x	xx.x, xx.x
Change from Baseline		
Mean (SD)	xx.xx (xx.xxx)	xx.xx (xx.xxx)
Median	xx.xx	xx.xx
Min, Max	XX.X, XX.X	xx.x, xx.x

Note: This summary uses all observed values; no missing data imputation is performed. Baseline is defined as the last available assessment on or prior to the first dose of study drug.

[1] For Screening and Week 0 the number of subjects with a value at the specified visit is displayed. For all post-baseline visits, the number of subjects with a value at baseline and at the specified visit is displayed. Source Data: Listing 16.2-7.1

Programming Note: present for Weeks 2, 6, 12, 18, 24, 36, 48, 60, 72, 84, 96, 97 and 1 week follow-up.

Protocol: THR-1442-C-418 Page x of y

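### SAP Table 2 counts a record as Screening only on or before Day -25, although Visit 1 may fall as late as Day -11, so some screening values drop out of the descriptive Screening summaries

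*SAP*

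**What the plan says.** **Schedule.** Footnote 1 of the SAP schedule (Table 1) reads "Screening period may last up to 21 days (V1 to V2), Run-in period is to be 14±3 days (V2 to V3". Protocol section 7 has the same rule: "Screening period may last up to 21 days (Visit 1 to Visit 2". Protocol 7.1.1, whose heading puts Visit 1 at weeks -5 to -2, adds: "The screening can be performed up to 3 weeks from the start of study activities". Each gives a maximum for screening. None gives a minimum.

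**Study day.** SAP 5.4.1 has no Day 0: "Note that the date of first dose is Day 1 and the day before the date of first dose is Day -1".

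**Slotting.** For all records, including unscheduled and repeat ones, SAP 5.4.2 says to "use the study day determined above with the slotting intervals in the analysis visit window table below to slot the record". Table 2 gives Screening a target of Day -35 and an interval of Day -25 or earlier. Week -2 has a target of Day -14 and an interval of Day -24 to Day -4. Under 5.4.3, if several records share a slot, the one closest to the target day is used. Nominal visit is only the second criterion, and it applies only within a slot.

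**Consequence of an unscheduled slot.** The text after Table 2 says that "if a value is slotted to a visit unscheduled for a parameter, it will not be summarized except for summaries focusing on extreme values". It then adds: "These records will also be included in data listings".

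**What is measured when.** The SAP schedule marks blood draws (HbA1c and FPG), the physical examination (which includes weight) and ECG at Visit 1 but not at Visit 2. Vital signs are marked at both.

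**Shells.** For HbA1c, Table 14.2-1.5 says "Use page 1 shell for Screening and Week 0", and the FPG shell, Table 14.2-2.5, matches it. The weight shell, Table 14.2-3.5, has a Screening page as its only pre-dose visit page. The blood pressure shells, Tables 14.2-4.5 and 14.2-5.5, have separate Screening, Week -2 and Week 0 pages.

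**The concern.** The Screening window is built around the longest nominal lead-in, whereas the schedule permits any shorter one. A subject who follows the protocol but moves quickly from Visit 1 to Visit 2 has the Visit 1 record labelled Week -2. For HbA1c, FPG, weight and ECG that slot is unscheduled, so the value leaves the by-visit summaries.

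The tables concerned are 14.2-1.5 (HbA1c), 14.2-2.5 (FPG), 14.2-3.5 (weight) and 14.2-6.3 (proportion below 7%), and possibly the ECG tables 14.3-4.2 and 14.3-4.3. Their Screening rows would describe a subset chosen by how slowly a site scheduled its visits, and nothing in the table would say so.

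Blood pressure has a second problem. Visits 1 and 2 then compete for one Week -2 slot, the subject is absent from the Screening page, and the reading kept as Week -2 may be the one from Visit 1.

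**Working it through.** **Inputs.** Let g be the days from Visit 1 to Visit 2: 0 to 21 (SAP Table 1, footnote 1; no minimum stated). Let v be the days from Visit 2 to Visit 3: 11 to 17 (14 ± 3). First dose is taken to be on the Visit 3 date.

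**Reproducing the plan's boundary.** Midpoint of the two targets: (-35 + -14)/2 = -24.5, which gives Day -25 or earlier against Day -24 or later, as printed. The same midpoint rule gives the later boundaries from Week 2/Week 6, (15 + 43)/2 = 29, to Week 84/Week 96, (589 + 673)/2 = 631. The Day -35 target is the nominal maximum, 21 + 14 = 35. The stated 102-week maximum duration agrees: 3 + 2 + 96 + 1 = 102.

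**Permitted Visit 1 days.** Visit 1 day = -(g + v). Earliest: -(21 + 17) = -38. Latest: -(0 + 11) = -11. That is 28 days, of which 14 (Day -38 to -25) slot to Screening and 14 (Day -24 to -11) slot to Week -2.

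**When a record is mis-slotted.** When g + v ≤ 24, that is g ≤ 24 - v.

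**Share of subjects.** The documents give no distribution for g. Assume it is spread evenly over whole days from a minimum to 21:

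| Visit 2 at | Mis-slotted if g is at most | Minimum 0 days | Minimum 3 days | Minimum 7 days |
|---|---|---|---|---|
| Day -11 | 13 | 14/22 = 64% | 11/19 = 58% | 7/15 = 47% |
| Day -14 | 10 | 11/22 = 50% | 8/19 = 42% | 4/15 = 27% |
| Day -17 | 7 | 8/22 = 36% | 5/19 = 26% | 1/15 = 7% |

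With a minimum of 14 days the share is 0% for every v, since 14 + 11 = 25. If every subject were screened within 7 days it would be 100%, since 7 + 17 = 24.

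**Blood pressure.** Take Visit 1 at Day -16 and Visit 2 at Day -11, a permitted pair. Both fall in the Week -2 slot. Their distances from Day -14 are 2 and 3 days, so the Visit 1 reading is kept as Week -2, the Visit 2 reading is set aside, and Screening is empty. If Visit 2 is at Day -14 or earlier, Visit 1 cannot be closer to the target, and the Visit 2 reading is kept.

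**Would another cut-off work?** Visit 2 spans Day -17 to Day -11, and Visit 1 may fall on those same days, so no single day separates them. A cut at Day -18 would never capture a Visit 2. With g even over 0 to 21 and v even over 11 to 17, it would still misplace the pairs with g + v ≤ 17: (7 + 6 + 5 + 4 + 3 + 2 + 1)/(22 × 7) = 28/154 = 18%.

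**The case against.** A reader might infer that a large share of screening data is lost. The documents do not support that. Half of the permitted days are affected, but the share of subjects runs from 0% to 100% with a screening interval that nobody states. The upper figures include same-day screening, which is not forbidden but fits poorly with the sequence: Visit 1 draws the laboratory tests on which eligibility depends, and Visit 2 confirms eligibility. This part of the objection stands.

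Nor are the values discarded. They remain in the listings and in extreme-value summaries such as shift tables, and Listing 16.2-7.1 shows both the visit and the analysis visit, so a screening HbA1c can still be identified. Visit 3 repeats HbA1c, FPG and ECG. Weight has no separate pre-dose page other than Screening, but the shell footnotes define baseline as the last assessment up to first dose, whatever its slot. A Visit 1 weight therefore still appears in the baseline block of Table 14.2-3.5 and in the demographics table. This stands too.

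The ECG shells 14.3-4.2 and 14.3-4.3 carry a note to use whatever time points the data contain, so it is unclear whether a Week -2 ECG would be suppressed there. They are possible cases only.

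A reader might also infer that stratification or eligibility is at risk because both use screening HbA1c. Neither passes through Table 2. The stratum is set at randomisation in the IWRS, and eligibility is decided at the visits.

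None of this removes the mechanism: under the rule as written, a compliant Visit 1 record can be assigned to the wrong visit.

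**Conclusion.** The point holds as a minor defect in descriptive tables. By rule, a Visit 1 record dated Day -24 to Day -11 is slotted to Week -2. Its HbA1c, FPG and weight values then leave the Screening summaries, and its ECG values may do so. Screening blood pressure is lost from its own page and can displace the Week -2 reading.

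The mechanism needs no assumption beyond first dose on the Visit 3 date. Its size does. Under an even spread with a minimum of 0 to 7 days and Visit 2 at Day -14, 27-50% of subjects are affected, or 80 to 150 of about 300 (300 × 4/15 and 300 × 11/22). The other permitted Visit 2 days move that range down to 7-36% or up to 47-64%, and a 14-day minimum makes it zero.

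The primary Week 24 analysis, the other efficacy tests, baseline and change from baseline do not use the Screening slot and are unaffected.

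**What to change.** In SAP 5.4.2, slot scheduled pre-dose records by nominal visit: Visit 1 to Screening, Visit 2 to Week -2, Visit 3 to Baseline. Assign an unscheduled or repeat pre-dose record to the nominal visit it repeats. Use the study-day windows of Table 2 only after first dose. The baseline definition in the shell footnotes can stay as it is.

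The cost is a few lines of SAP text and a small programming change. The rule for repeats is the one real addition. Pure nominal slotting would leave them unassigned, and they are to be expected, since Protocol 7.1.1 brings unfasted subjects back within a week.
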